8.3. Exploratory Efficacy Endpoints

Exploratory efficacy endpoints are defined in Section 3.2.3. No formal assessment of difference between treatment groups will be performed for any of the exploratory efficacy endpoints. The difference between treatment groups in exploratory efficacy endpoints will be estimated with 95% CIs to quantify the treatment effect.

Summary tables presenting observed values and changes from baseline for NT-proBNP measurement concentration (pg/mL), cardiac output (L/min), cardiac index (L/min/m²), mRAP (mmHg), mPAP (mmHg), and PAWP (mmHg) will be provided for each treatment group by scheduled visits using descriptive statistics. The difference in the change from baseline between treatment groups with 95% CIs will be estimated non-parametrically using Hodges-Lehmann estimation of location shift in the tables. The analyses will be based on the PEA set and the PPS.

Hospital length of stay in days and ICU length of stay in days will be summarised using descriptive statistics. The difference between treatment groups with 95% CI will be estimated non-parametrically using Hodges-Lehmann estimation of location shift in the table. The analyses will be based on the PEA set.

Time from start of ICU stay to end of mechanical ventilation (in hours) will be analysed using the Kaplan Meier method. Median and quartiles in days and associated 95% CI will be calculated using the LOGLOG transformation. All patients stayed in ICU who do not have end date of mechanical ventilation will be censored at the time of discharged from the ICU. The analyses will be based on the PEA set.

Proportion of in-hospital mortality will be summarised using the frequency counts and percentages for the PEA set. Proportion difference between treatment groups along with the Clopper-Pearson exact CI will be provided

The proportion of patients who need PAH-targeted therapy immediately after PEA to Visit 4 will be summarised using the frequency counts and percentages for the PEA set and the PPS. Proportion difference between treatment groups along with the Clopper-Pearson exact CI will be provided.

WHO functional class will be summarised by scheduled visit for each treatment group. Shift table of baseline functional class versus functional class at each postbaseline scheduled visit will be provided. The analyses will be based on the PEA set and the PPS.

9. Safety Analysis

The purpose of this section is to define the safety analyses for the study. Safety assessments include adverse events, vital sign measurements, ECG measurements, physical examination, clinical laboratory examination, and pregnancy testing. Safety assessments will be performed at time points specified in Schedule of Events (Appendix 13.1). All summaries of safety data will be conducted using the safety set.

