Pulmonary endarterectomy is the surgical procedure that removes the obstructing thromboembolic material, resulting in significant improvements (or normalisation) in pulmonary haemodynamics and right ventricular function. Pulmonary endarterectomy targets the accessible mechanical component contributing to PH and is a potentially curative treatment in CTEPH. Long-term survival and functional status were demonstrated to improved post-PEA (Cannon *et al* 2016). Accordingly, careful patient selection and complete and thorough endarterectomy are critical for the best outcome from PEA. However, even from experienced centres, the perioperative mortality rate was 4.7% (Pepke-Zaba *et al* 2011). This risk is higher in patients with high preoperative PVR (Jensen *et al* 2009). In the European CTEPH registry, an almost linear relationship between high preoperative PVR ($>900\text{--}1100\text{ dyn}\cdot\text{s}\cdot\text{cm}^{-5}$) and in-hospital mortality was observed (Mayer *et al* 2011). An important cause of the high PVR and postoperative mortality can be linked

to the concomitant small vessel disease in CTEPH (Galiè and Kim 2006). The long-term prognosis of operable patients is nowadays excellent and better than the outcome of inoperable patients (Delcroix et al 2016).

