4.3.3 Replacements

A total of 88 patients will be randomly assigned in the study with a target of 80 patients completing the study with an assumption of a 10% dropout rate.

Therefore, drop out for any reason before the last follow-up visit (Visit 4) will be monitored continuously throughout the study, and patients that drop out will be replaced to make a total number of 88 randomised patients. In case of a high initial dropout rate, the DSMB and the sponsor will evaluate the reasons for drop out and decide in mutual agreement on potential extension of further randomisations.

5 Study Drugs

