7.3 Exploratory Efficacy Endpoints

A Visit 2 assessment is considered as valid only when the assessment is completed within 7 days prior to the PEA. For assessments at Visit 4, the nominal visit collected in eCRF will be used in the analysis. This rule is applicable to all endpoints derived by the visit. The exploratory efficacy endpoints are mentioned below.

1. NT-proBNP measurement concentration change from baseline at the preoperative visit (Visit 2) and at 6 months after PEA (Visit 4)
2. Cardiac index change from baseline at the preoperative visit (Visit 2) and at 6 months after PEA (Visit 4)
3. Mean right atrial pressure change from baseline at the preoperative visit (Visit 2) and at 6 months after PEA (Visit 4)
4. Mean pulmonary arterial pressure change from baseline at the preoperative visit (Visit 2) and at 6 months after PEA (Visit 4)
5. Pulmonary artery wedge pressure change from baseline at the preoperative visit (Visit 2) and at 6 months after PEA (Visit 4)
6. Hospital length of stay

The hospital length of stay in days will be derived from the first date when the patient is hospitalised for PEA until the date when the patient is discharged from the hospital.

7. ICU length of stay in days
8. Time on mechanical ventilation, in hours, from start of ICU stay until end of mechanical ventilation
9. In-hospital mortality

Only deaths that happen on or after PEA but before discharge from the hospital will be included.

10. Functional class at the preoperative visit (Visit 2) and at 6 months after PEA (Visit 4)

11. Need for PAH-targeted postoperative therapy at the 6-month visit (Visit 4)

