- When frequency counts are presented, the percentage will be suppressed when the count is zero in order to draw attention to the non-zero counts. A row denoted “Missing” will be included in count tabulations where specified on the shells to account for dropouts and missing values. Percentages will be based on the total number of patients in the respective analysis set unless otherwise specified.
- Unless otherwise specified, statistical tests will be 2-sided and performed using a 5% significance level, leading to 95% (2 sided) confidence intervals (CIs). Modelling techniques will be used in an exploratory sense. No adjustments for multiplicity are made.
- Partial dates will be imputed based on the rules specified in Appendix 13.4.
- All laboratory data will be reported by using the International System of Units.
- Unless otherwise specified, the baseline will be defined as the last valid assessment, including assessments from the unscheduled visit, prior to the study drug administration.
- A Visit 2 assessment is considered as valid only when the assessment is completed within 7 days prior to PEA. For assessments at Visit 4, the nominal visit collected in electronic case report form (eCRF) will be used in the analysis. This rule is applicable to all endpoints derived by the visit.
- By-patient listings will be created for each eCRF module for all screened patients. Patients will be identified in the listings by patient number. If data are to be summarised by visit, the visit name collected on the eCRF page will be used.
- All analyses will be conducted using SAS® software Version 9.3 or later (SAS Institute Inc, Cary, North Carolina).

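### NT-proBNP is compared only as unadjusted absolute change in pg/mL; if it falls substantially in both arms after PEA, the Visit 4 interval is valid but imprecise for a proportional effect

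*SAP*

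**What the plan says.** Protocol 7.3 defines the endpoint as "NT-proBNP measurement concentration change from baseline at the preoperative visit (Visit 2) and at 6 months after PEA (Visit 4"). SAP 3.2.3 repeats it. SAP 8.3 gives the only analysis: "Summary tables presenting observed values and changes from baseline for NT-proBNP measurement concentration (pg/mL"), by arm and visit, with the arm difference in change "estimated non-parametrically using Hodges-Lehmann estimation of location shift in the tables", on the PEA set and the PPS.

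Change here means absolute change. SAP section 4 speaks of differences to baseline, and SAP 8.1 lists change and percent change as two separate quantities for PVR. Neither document gives NT-proBNP a log scale, a percent change or a baseline covariate. PVR has both percent change and a supportive ANCOVA on baseline (SAP 8.1).

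On status, SAP 8.3 states: "No formal assessment of difference between treatment groups will be performed for any of the exploratory efficacy endpoints". It adds that the differences will be estimated with 95% CIs to show the size of the treatment effect.

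**The concern.** By Visit 4 both arms have had an operation that protocol 1.1 describes as "resulting in significant improvements (or normalisation) in pulmonary haemodynamics and right ventricular function". If NT-proBNP follows, most of the starting concentration disappears in every patient, and a patient's absolute change is largely set by where that patient started. A proportional effect of riociguat acts only on the small remainder. The Hodges-Lehmann estimator protects against outliers but does not remove variation that comes from baseline. Randomisation is unstratified (SAP 4.2), so baseline NT-proBNP is balanced only by chance.

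What is at stake is how informative the Visit 4 estimate and interval are. The study asks whether treatment before PEA improves outcomes after it (protocol 3.1.1), and NT-proBNP is the only blood marker among the efficacy endpoints. A wide interval centred on a noisy shift would say little either way.

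**Working it through.** **Figures from the documents.** Protocol 4.3.3: "A total of 88 patients will be randomly assigned in the study with a target of 80 patients completing the study". With 10% dropout, 80 × 1.10 = 88, which reproduces the plan's number (80/0.90 = 88.9 would give 89). With 1:1 allocation that is 40 completers per arm. SAP section 4 sets two-sided 5% tests and 95% intervals. No power, level, SD or effect is stated for NT-proBNP, so there is no NT-proBNP figure to reproduce.

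**Assumed, not in the documents.** Log-normal values with median 1500 pg/mL and log SD 1.0 at both times; log-scale correlation ρ between baseline and follow-up of 0.3 to 0.7; true riociguat/placebo ratio 0.7; a common fall of 80%, 50% or none.

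**Size of the signal on the planned scale.** If follow-up is a fraction f of baseline and riociguat multiplies it by 0.7, the treatment effect on absolute change is about (1 − 0.7) × f = 0.3f of baseline:
- 80% fall: 0.3 × 0.2 = 6% of baseline
- 50% fall: 0.3 × 0.5 = 15%
- no fall: 0.3 × 1 = 30%

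**How much of the estimate is baseline imbalance.** Across simulated trials with a 60-80% fall (grid: log SD 0.8 to 1.3, ratio 0.6 or 0.7), the shift in change correlates −0.77 to −0.98 with the shift in baseline. Squared, 0.77² = 0.59 and 0.98² = 0.96, so 59-96% of its variation is baseline imbalance. At log SD 1.0 and ratio 0.7, a 50% fall gives −0.78 (61%). With no fall and ρ = 0.7 it is −0.44 (19%).

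**Central case (80% fall, ρ = 0.5, ratio 0.7).** The mean shift is −145 pg/mL with SD 291. The ratio 145/291 is 0.50, so the estimate should have the wrong sign in about Φ(−0.50) = 31% of trials; the simulation also gave 31%. With no true effect the mean shift is about 1 pg/mL and the interval excludes zero in 4.8% of trials. The planned method is therefore unbiased with a correct error rate.

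**Share of trials whose 95% CI excludes no effect** (ratio 0.7, log SD 1.0, ρ 0.3 to 0.7; the Hodges-Lehmann interval represented by the matching rank-sum test):

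| Common fall | Planned absolute change | ANCOVA of log value on log baseline |
|---|---|---|
| 80% | 7-8% | 38-56% |
| 50% | 13-18% | 36-62% |
| None, as at Visit 2 | 22-35% | 38-56% |

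**Check of the right-hand column.** The effect is ln 0.7 = −0.357, and the standard error is √(1 − ρ²) × √(2/40):
- ρ = 0.3: 0.954 × 0.2236 = 0.213; 0.357/0.213 = 1.67; Φ(1.67 − 1.96) ≈ 39%
- ρ = 0.5: 0.866 × 0.2236 = 0.194; 0.357/0.194 = 1.84; Φ(1.84 − 1.96) ≈ 45%
- ρ = 0.7: 0.714 × 0.2236 = 0.160; 0.357/0.160 = 2.23; Φ(2.23 − 1.96) ≈ 61%

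A common fall cancels on the log scale, so these values apply to all three rows. The differences between rows in that column are simulation noise. The differences in the planned column come from the fall.

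**Wider grid** (log SD 0.8 to 1.3, ratio 0.6 or 0.7, fall 60-80%): 6-28% for absolute change against 23-97% for log ANCOVA. With log SD 1.3 and ratio 0.7, log ANCOVA reaches only 23-40%.

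**The case against.** The strongest reply is about status. NT-proBNP is one of eleven exploratory endpoints, formal comparison is ruled out, and the sample size disclaims power (protocol 7.5). No conclusion of the trial depends on this table. That stands, and it limits the severity. It does not settle the matter, because SAP 8.3 still offers the interval as a measure of the treatment effect, and the point concerns the precision of that measure.

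The inputs are assumed. Protocol 1.1 speaks of haemodynamics and right ventricular function, not of NT-proBNP or any percentage fall. This stands, so every figure is conditional.

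A lasting effect at Visit 4 may not exist. Study drug stops at PEA, nominally 276 − 96 = 180 days earlier. Protocol 3.1.1 reports no post-PEA haemodynamic difference in the randomised bosentan pretreatment study. Visit 2 is the on-drug comparison, and the loss there is smaller. This is fair, but Visit 4 is a planned time point and its interval should be as informative as the data allow.

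A plain log ratio is not a full remedy. When follow-up is imperfectly correlated with baseline, the unadjusted log ratio keeps some dependence on baseline and detects only 24-48% at an 80% fall. This stands, and it is why the covariate is needed.

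Observed Visit 4 values are tabulated by arm, which helps a reader, but no between-arm interval is planned for them. Absolute change also follows the protocol's wording and matches the other exploratory haemodynamic measures, so a new analysis should be recorded as a change.

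**Conclusion.** The point holds as a minor one. The only planned arm comparison of NT-proBNP is unadjusted absolute change. If the marker is skewed and falls substantially after PEA, that comparison is much less precise at Visit 4 for a proportional effect than a baseline-adjusted log analysis. Under the stated assumptions the loss is large at an 80% fall, clear at 50%, and smaller with no common fall.

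A reader might infer three stronger things that the documents do not support:
- That a real effect would be nearly undetectable. This fits only a fall near 80%, and no fall is given.
- That the Visit 4 result is biased by baseline or would produce false findings. Randomisation leaves no systematic difference, and the error rate under no effect is 4.8%; the interval is simply wide.
- That the log scale would secure detection. In the main scenario it reaches only 36-62%, and less with greater spread.

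The size rests on log-normal values, a proportional effect, equal spread before and after, and 40 evaluable patients per arm.

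**What to change.** In SAP 8.3, add an analysis of log NT-proBNP at Visit 2 and at Visit 4 with treatment as factor and log baseline as covariate, in the PEA set and the PPS. Report the adjusted ratio of geometric means, riociguat to placebo, with its 95% CI. The covariate should be mandatory. Keep the pg/mL summary as description. List the addition in SAP section 11, and settle it before database lock and unblinding so that the scale is not chosen after seeing the results.

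No new data are needed: NT-proBNP is already collected at Visits 1, 2 and 4. The cost is one extra table and a documented departure from the protocol's change-from-baseline wording.

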6.2.16 Time on Mechanical Ventilation

The total time spent on mechanical ventilation from the start of the ICU stay until end of mechanical ventilation during Visit 3 will be reported for each patient.

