3.2.3. Exploratory Efficacy Endpoints

The exploratory efficacy endpoints are mentioned below.

1. NT-proBNP measurement concentration change from baseline at the preoperative visit (Visit 2) and at 6 months after PEA (Visit 4)
2. Cardiac index change from baseline at the preoperative visit (Visit 2) and at 6 months after PEA (Visit 4)
3. Mean right atrial pressure (mRAP) change from baseline at the preoperative visit (Visit 2) and at 6 months after PEA (Visit 4)
4. Mean pulmonary arterial pressure (mPAP) change from baseline at the preoperative visit (Visit 2) and at 6 months after PEA (Visit 4)
5. Pulmonary artery wedge pressure (PAWP) change from baseline at the preoperative visit (Visit 2) and at 6 months after PEA (Visit 4)
6. Hospital length of stay

The hospital length of stay in days will be derived from the first date when the patient is hospitalised for PEA until the date when the patient is discharged from the hospital.

7. ICU length of stay in days
8. Time on mechanical ventilation, in hours, from start of ICU stay until end of mechanical ventilation
9. In-hospital mortality

Only deaths that happen on or after PEA but before discharge from the hospital will be included.

10. Functional class at the preoperative visit (Visit 2) and at 6 months after PEA (Visit 4)
11. Need for PAH-targeted postoperative therapy from immediately after PEA to the 6-month visit (Visit 4)

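### Time on mechanical ventilation is analysed by Kaplan-Meier with no provision for death, so an arm with early deaths has its share off the ventilator overstated and its upper quartile understated

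*SAP*

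**What the plan says.** **Ventilation.** The protocol (6.2.16) defines the quantity as "The total time spent on mechanical ventilation from the start of the ICU stay until end of mechanical ventilation during Visit 3". SAP 8.3 sets the method: "Time from start of ICU stay to end of mechanical ventilation (in hours) will be analysed using the Kaplan Meier method". The median and quartiles are to be reported with 95% confidence intervals, in the PEA set. Patients who stayed in the ICU and "who do not have end date of mechanical ventilation will be censored at the time of discharged from the ICU". Neither document says what happens to a patient who dies on the ventilator.

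**Stay.** SAP 3.2.3 runs hospital stay from admission for PEA "until the date when the patient is discharged from the hospital". ICU stay is listed only as "ICU length of stay in days", with no start, end or death rule. For both stays, SAP 8.3 says: "The difference between treatment groups with 95% CI will be estimated non-parametrically using Hodges-Lehmann estimation of location shift in the table".

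**Death and status.** SAP 8.3 also reports death in the same patients: "Proportion of in-hospital mortality will be summarised using the frequency counts and percentages for the PEA set", with a difference between arms. All these endpoints are exploratory: "No formal assessment of difference between treatment groups will be performed for any of the exploratory efficacy endpoints".

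**The concern.** Kaplan-Meier censoring assumes that a censored patient has the same future chance of the event as those still under observation. That is reasonable for a patient transferred out while still ventilated. It is not reasonable for a patient who has died, because extubation can no longer happen. Death here is a competing event.

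A missing ventilation end date at ICU exit may often mean death, so the rule would act on the patients with the worst outcome. Protocol 1.1 cites a perioperative mortality of 4.7% and says the risk is higher with high preoperative PVR. Entry requires PVR above 800 dyn·s·cm⁻⁵, so some deaths should be expected.

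What is at stake is the between-arm reading of one perioperative recovery measure, in a trial with a secondary objective about safety and efficacy during PEA. The primary endpoint is not touched.

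**Working it through.** The plan states no figure for ventilation, so there is nothing to reproduce on that endpoint.

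**Inputs from the documents.** 88 randomised 1:1 (44 per arm) with a target of 80 completers (40 per arm); mortality 4.7%.

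**Assumptions.** 42 operated per arm (between 40 and 44). Ventilation time is log-normal with median 36 h and log-SD 0.9. Deaths occur on the ventilator and the patient leaves the ICU at death. The documents give none of these.

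**Step 1: expected deaths.** At 4.7%, 40 × 0.047 = 1.9 and 44 × 0.047 = 2.1 per arm. The chance of at least one death in an arm is 1 − 0.953^40 = 85% to 1 − 0.953^44 = 88%. At an assumed 10%, 4.0 to 4.4 deaths per arm.

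**Step 2: share off the ventilator by 96 h, all deaths at 48 h.** Under the log-normal, Φ(ln(48/36)/0.9) = 62.5% are off by 48 h and Φ(ln(96/36)/0.9) = 86.2% by 96 h. Counts are rounded to whole patients.

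- Kaplan-Meier: 1 − (ventilated just before the deaths / 42) × (still ventilated at 96 h / at risk after the deaths).
- Cumulative incidence: number extubated by 96 h / 42.

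| Case | Off by 48 h | At risk after 48 h | Off 48–96 h | Kaplan-Meier | Cumulative incidence |
|---|---|---|---|---|---|
| No deaths | 26 | 16 | 10 | 36/42 = 85.7% | 85.7% |
| 4 deaths, unrelated to ventilation time | 24 | 14 | 9 | 1 − (18/42)(5/14) = 84.7% | 33/42 = 78.6% |
| 4 deaths, longest-ventilated patients | 26 | 12 | 10 | 1 − (16/42)(2/12) = 93.7% | 36/42 = 85.7% |
| 2 deaths, unrelated | 25 | 15 | 9 | 1 − (17/42)(6/15) = 83.8% | 34/42 = 81.0% |
| 2 deaths, longest-ventilated | 26 | 14 | 10 | 1 − (16/42)(4/14) = 89.1% | 36/42 = 85.7% |

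The overstatement is 6 to 8 points with 4 deaths and about 3 points with 2 deaths (42 × 0.047 = 2.0).

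**Step 3: upper quartile, which the SAP does report (4 deaths at 48 h).**

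- Unrelated deaths, Kaplan-Meier: (18/42)(1 − x/14) = 0.25 gives x = 5.83. The quantile is (24 + 5.83)/38 = 0.785, so 36·exp(0.9 × 0.789) = 73.3 h.
- Unrelated deaths, cumulative incidence: 0.75 × 42 = 31.5, and 31.5/38 = 0.829, so 36·exp(0.9 × 0.950) = 84.7 h. Kaplan-Meier is 11.4 h too short.
- Longest-ventilated, Kaplan-Meier: (16/42)(1 − x/12) = 0.25 gives x = 4.125. The quantile is 30.125/42 = 0.717, so 36·exp(0.9 × 0.575) = 60.4 h.
- Longest-ventilated, cumulative incidence: 36·exp(0.9 × 0.674) = 66.1 h. Kaplan-Meier is 5.7 h too short.

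**Step 4: sensitivity to timing.** Simulation, 40 per arm, 2,000 replicates, 4 deaths. Each pair is the SAP method against death counted as never extubated.

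| Deaths | Off by 96 h | Upper quartile (h) | Median (h) |
|---|---|---|---|
| 6–36 h, random | 86% v 78% | 68.3 v 80.8 | 37.4 v 39.4 |
| 6–36 h, sickest | 95% v 85% | 55.8 v 63.2 | 33.5 v 34.8 |
| 24–120 h, random | 81% v 77% | 79.1 v 81.8 | 39.8 v 39.8 |
| 24–120 h, sickest | 90% v 86% | 62.9 v 63.9 | 34.7 v 34.7 |
| 10–30 days, random | 78% v 78% | 80.6 v 80.6 | 39.6 v 39.6 |
| 10–30 days, sickest | 86% v 86% | 63.8 v 63.8 | 34.9 v 34.9 |

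With no deaths the share off by 96 h is 86%. If a site enters the death date as the end of ventilation, which nothing forbids, the median for 6–36 h deaths among the sickest falls to 29.3 h.

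**Step 5: hospital stay.** Assumed log-normal with median 14 days and log-SD 0.5; 4 deaths in one arm and none in the other. The Hodges-Lehmann shift is −1.2 to −1.3 days if stay ends at an early or mid death, about 0 if the stay is missing (and unrelated to the risk of death), +0.5 days for late deaths, and about +1.3 days if deaths are ranked worst.

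**The case against.** The strongest reply is that a reader will see the deaths anyway. In-hospital mortality is tabulated by arm in the same PEA set, all-cause death has its own analysis, and ventilation beyond 96 h is a listed surgical complication compared by Fisher's exact test. The endpoint is exploratory and has no formal test. The SAP reports the median and quartiles, not the share at 96 h, and the median hardly moves. All of this stands and lowers the stakes. It does not correct the ventilation curve or its upper quartile, and SAP 8.3 offers the exploratory estimates as a measure of the treatment effect.

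A reader might infer that more deaths in general make an arm look faster. The calculations do not support that. Deaths unrelated to ventilation time leave the Kaplan-Meier share close to the no-death value (84.7% against 85.7%), so they are hidden but not rewarded. The arm looks faster only when early deaths fall on the sickest patients. Late deaths make no difference.

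A reader might also infer that patients who die are given a short or missing hospital stay. The SAP does not say so; it is silent. The shift can be negative, nil or positive depending on an unstated convention and on when deaths occur. Ranking deaths worst is a choice of estimand, so its result is not the true value against which the others are wrong.

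**Conclusion.** The point holds for ventilation time. Applied to patients who die ventilated, the SAP's rule treats a competing event as ordinary censoring. With 4 deaths by 48 h among 42 patients, roughly 85 to 95% appear off the ventilator by 96 h, against 79 to 86% by cumulative incidence. The upper quartile is about 5 to 15 h too short and the median changes little. At 4.7% mortality the effect is about half. These sizes rest on the assumed log-normal times and on deaths being early; with deaths spread over 24 to 120 h the upper-quartile error is only about 1 to 3 h.

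Hospital and ICU stay have a gap in specification, not a demonstrated bias. Because the endpoints are exploratory and mortality is reported separately, this is a change to consider.

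**What to change.** **Ventilation.** In SAP 8.3, replace Kaplan-Meier with the cumulative incidence of extubation. Death before extubation is a competing event: it is neither censored nor counted as the end of ventilation. Take the median and quartiles from that curve, and state that a quartile is not reached if too few patients are extubated. Keep censoring at ICU exit only for patients who leave alive and still ventilated. If every patient is followed to extubation or death, the curve is simply the number extubated by each time divided by the number analysed. In the same edit, reconcile the units: SAP 8.3 gives the endpoint in hours and its median and quartiles in days.

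**Stay (secondary clarification).** State before unblinding that a death date is not to be used as a discharge date. Present survivors' hospital and ICU stay beside in-hospital mortality. A worst-rank analysis can be added as an optional sensitivity analysis.

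**Cost.** A few lines of SAP text and a standard method; no new data beyond the extubation, ICU exit, discharge and death dates. The cumulative incidence curve is slightly harder to explain, because it combines the speed of extubation with survival to extubation. Survivors' stay compares groups selected after randomisation, so it must be read together with mortality.
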